### 6.2 Management of Palbociclib Dose Reductions

Dose reductions for palbociclib are outlined in **Table 1**.

**Table 1:** Palbociclib dose modifications for adverse reactions

Cohort A	
Dose Level	Dose of Palbociclib
Starting dose	100 mg daily
First dose reduction	75 mg daily
Cohort B	
Dose Level	Dose of Palbociclib
Starting dose	125 mg daily
First dose reduction	100 mg daily
Second dose reduction	75 mg daily

### 6.3 Management of Ganitumab Dose Reductions

Dose reductions for ganitumab are outlined in **Table 2**.

**Table 2:** Ganitumab dose modifications for adverse reactions

Dose Level	Dose of Ganitumab
Starting dose	18 mg/kg on days 1 and 15
First dose reduction	12 mg/kg on days 1 and 15

## 6.4 Dose Modifications for Non-Hematologic Toxicity

### 6.4.1 Management of QTc Prolongation

QTc prolongation is a potential risk of palbociclib. In the setting of QTc prolongation, treat reversible causes such as serum electrolyte abnormalities and/or reduce usage of concomitant QTc-prolonging medications. See **Table 3** for recommended dose modifications in the setting of QTc prolongation.

**Table 3:** Palbociclib dose modifications for prolonged QTc

	Grade 2 QTc prolongation	Grade 3 QTc prolongation	Grade 4 QTc Prolongation
Reversible cause identified	Treat reversible causes  Initiate more frequent ECG monitoring according to investigator's best medical judgement until QTc < 480 msec  Continue at the same dose level	Treat reversible causes  Withhold treatment until QTc < 501 msec  Resume treatment at same dose  Initiate more frequent ECG monitoring according to investigator's best medical judgement until QTc < 480 msec	Remove from protocol therapy
No reversible cause identified	Initiate more frequent ECG monitoring according to investigator's best medical judgement until QTc < 480 msec  Continue at the same dose level	Withhold treatment until QTc < 501 msec  Resume treatment at one dose level below the current dose unless the patient has had two dose reductions of palbociclib in which case the patient must	Remove from protocol therapy

		
be removed from protocol therapy
 
Initiate more frequent ECG monitoring according to investigator's best medical judgement until QTc < 480 msec
	
--	--	---	--

#### 6.4.2 Management of Hyperglycemia

For patients who develop hyperglycemia (based on random, non-fasting glucose levels), discontinue use of corticosteroids before modifying ganitumab dose. If hyperglycemia occurs without use of corticosteroids, ganitumab therapy modifications should be as follows:

Hyperglycemia Grade (per CTCAE, under Hyperglycemia )	Action
Grade 1	Continue ganitumab.
Grade 2	Continue ganitumab. Consider consultation with Pediatric Endocrinologist.
Grade 3 or Urine glucose > 0.1 g/dL	
 
Initiate insulin therapy or oral diabetic agent* as indicated.
 
Hold ganitumab until resolves to <math>\leq</math> Grade 2 without glycosuria.
 
Resume ganitumab at same dose IF patient is asymptomatic, AND serum glucose is consistently <math><</math> 250 mg/dL (<math>\leq</math> Grade 2) without glycosuria AND resolution to <math>\leq</math> Grade 2 has occurred within 2 weeks of interruption. The patient may continue to receive concomitant insulin or an oral diabetic agent for the management of hyperglycemia while receiving ganitumab.
 
If Grade 3 hyperglycemia recurs despite a stable dose of insulin or oral diabetic agent OR if resolution to consistent levels <math>\leq</math> Grade 2 requires more than 2 weeks of interruption, subsequent doses should be administered with a reduced dose of 12 mg/kg/dose.
 

Grade 4	
 
Initiate insulin therapy as indicated.
 
If associated with diabetic ketoacidosis or hyperosmolar nonketotic syndrome, discontinue ganitumab permanently. Otherwise, use the following instructions.
 
Hold ganitumab until resolves to <math>\leq</math> Grade 2.
 

	
 
Resume ganitumab with a reduced dose of 12 mg/kg/dose IF patient is asymptomatic, AND serum glucose is consistently <math>< 250</math> mg/dL (<math>\leq</math> Grade 2) without glycosuria AND resolution to <math>\leq</math> Grade 2 has occurred within 2 weeks of interruption. The patient may continue to receive concomitant insulin or an oral diabetic agent for the management of hyperglycemia while receiving ganitumab.
 
If resolution to consistent levels <math>\leq</math> Grade 2 requires more than 2 weeks of interruption OR if Grade 4 toxicity recurs after re-challenge with 12 mg/kg, then discontinue ganitumab permanently.
 

--	---

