### 3.2 Exclusion Criteria

3.2.1 Patients must not be receiving any of the following concomitant medications:

3.2.1.1 Pharmacologic doses of systemic corticosteroids unless for CNS metastatic disease. For patients with CNS metastatic disease receiving corticosteroids, they should be on a stable or decreasing dose over the 7 days prior to registration and meet criteria in Section 3.1.6.7.

For all patients, receipt of systemic physiologic replacement steroids, topical and/or inhaled corticosteroids is acceptable.

3.2.1.2 Patients receiving medications that are strong inhibitors or inducers of CYP3A4 within 7 days of enrollment (refer to Appendix B, **Table 10** for prohibited medications)

3.2.1.3 Patients receiving medications that cause significant QTc prolongation as outlined in **Table 12** of Appendix B.

3.2.2 Patients who have had tumor molecular testing with sequencing of the RB1 gene and were found to have RB1 mutation or loss will be excluded.

3.2.3 Patients with a history of pneumonitis will be excluded.

3.2.4 Pregnant participants will not be entered on this study given that the effects of palbociclib and ganitumab on the developing human fetus are unknown.

3.2.5 Because there is an unknown but potential risk for adverse events in nursing infants secondary to treatment of the mother with palbociclib and ganitumab, breastfeeding mothers are not eligible.

3.2.6 Participants of child-bearing or child-fathering potential must agree to use adequate contraception (hormonal birth control; intrauterine device; double barrier method; or total abstinence) throughout their participation, including up until 30 days after last dose of palbociclib or ganitumab, whichever was administered last.

3.2.7 History of allergic reactions attributed to compounds of similar chemical or biologic composition to palbociclib or ganitumab.

3.2.8 Uncontrolled intercurrent illness including, but not limited to, ongoing or active infection, symptomatic congestive heart failure, unstable angina pectoris, cardiac arrhythmia, or psychiatric illness/social situations that would limit compliance with study requirements.

3.2.9 Participants with a personal history of any of the following: syncope due to an intrinsic cardiac etiology (note that syncope due to vasovagal episodes or dehydration/orthostasis would NOT exclude a participant), pathologic ventricular arrhythmias (including, but not

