#### Definition of Dose-Limiting Toxicity

DLT is defined as any of the following events that are possibly, probably or definitely attributable to palbociclib or ganitumab. A DLT may occur in any cycle and will guide dose modifications, but only DLTs occurring in the first cycle will be used for implementation of the safety monitoring rule (Section 13.4).

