## 5.5 General Concomitant Medication and Supportive Care Guidelines

### 5.5.1 Concomitant Medications

- 5.5.1.1 No other cancer chemotherapy or anticancer therapies are allowed except local measures specified in section 5.3.3.
- 5.5.1.2 Appropriate antibiotics, blood products, anti-emetics, fluids, electrolytes and general supportive care are to be used as necessary (see Section 5.5.2).
- 5.5.1.3 Patients may not receive corticosteroids EXCEPT under the following conditions:
  - Physiologic replacement for patients with adrenal insufficiency
  - As needed to manage allergic reactions
  - To prevent transfusion reactions
  - Inhaled or topical administration
  - In patients with metastatic CNS disease, use of doses that have been stable or tapering since enrollment.
- 5.5.1.4 Subjects must not receive any of the QT prolonging agents in Appendix B, Table 12. QT prolonging agents in Appendix B, Table 13 are to be used with caution.
- 5.5.1.5 Subjects must not receive strong CYP3A inducers or inhibitors (delineated in Appendix B, Table 10) within 7 days of enrollment and while on protocol therapy. Subjects receiving moderate CYP3A inhibitors should be monitored (see Appendix B, Table 11).

Subjects receiving concomitant medications metabolized by CYP3A enzymes should be monitored at the discretion of the investigator, particularly if the concomitant medication has a narrow therapeutic window and/or is known to rely strongly on one of these isoenzymes for its metabolism. Such medications may have an interaction with palbociclib.

Patients must avoid consumption of grapefruit products, and Seville oranges or products containing the juice of each while on protocol therapy, due to potential CYP3A4 interaction with the study medications. Orange juice is allowed.

Please refer to the palbociclib and ganitumab Investigator's Brochures for additional drug interaction information.

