### 6.1 Dose Modification for Dose-Limiting Toxicity

Patients with protocol-defined DLT (Section 5.4.1) will have palbociclib and ganitumab held. Except where noted below for specific target toxicities, palbociclib and ganitumab will be held until resolution of toxicity to  $\leq$  Grade 1 (or baseline, whichever is higher grade), and then palbociclib and ganitumab will be resumed with dose reduction according to Sections 6.2 (palbociclib) and 6.3 (ganitumab). If a patient cannot resume therapy within 21 days of holding palbociclib and ganitumab, they will be removed from protocol therapy.

Patients with recurrent DLT (regardless of category of DLT) despite this dose reduction are eligible for up to one additional dose reduction of palbociclib. Patients with recurrent DLT despite two dose reductions of palbociclib will be removed from protocol therapy. If a second dose reduction is required for toxicity related to ganitumab, the patient will be removed from protocol therapy.

Patients who meet criteria for permanent discontinuation of one study agent (e.g., severe allergic reaction), will be removed from protocol therapy altogether rather than continuing with monotherapy.

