#### 6.4.3 Management of ganitumab-related infusion reactions

For patients who have allergic or acute infusion reactions, therapy modifications based on grade should be as follows. Guidelines for emergency management of infusion reactions are recommendations and institutional standard practice may be used as an alternative.

Grade	Action
Grade 1 Transient flushing or rash, drug fever $< 38^{\circ}\text{C}$ ( $< 100.4^{\circ}\text{F}$ )	
 
Slow infusion rate by 50% and monitor patient for worsening of condition. Maximum infusion duration is 120 minutes.
 

Grade 2 Rash, flushing, urticaria, dyspnea, drug fever $\geq 38^{\circ}\text{C}$ ( $\geq 100.4^{\circ}\text{F}$ )	
 
Stop infusion; symptom control (diphenhydramine hydrochloride 1 mg/kg (max 50 mg) IV, acetaminophen 10-15 mg/kg (max 650 mg) PO or IV for fever, and oxygen if needed).
 
Resume infusion at 50% of the prior rate once the reaction has decreased to <math>\leq</math> Grade 1. Monitor patient for worsening condition. Maximum infusion duration is 120 minutes.
 
For subsequent dose, premedicate with diphenhydramine hydrochloride 1 mg/kg (max 50 mg) IV.
 
If Grade 1-2 infusion reactions reoccur with subsequent dose, add dexamethasone 0.2 mg/kg (max 10 mg) IV or equivalent to premedications above. (Only dose interruption/discontinuation, but not dose reduction, is required for allergic/infusional reactions.)
 

Grade 3 Symptomatic bronchospasm with or without urticaria, allergy-related edema/angioedema, hypotension	

Stop infusion immediately.

Administer diphenhydramine hydrochloride 1 mg/kg (max: 50 mg) IV, dexamethasone 0.2 mg/kg (max: 10 mg) IV (or equivalent), bronchodilators for bronchospasms, and other medications as medically indicated. Hospital admission should be considered.

Discontinue ganitumab treatment permanently.

Grade 4 Anaphylaxis	

Stop infusion immediately

Administer diphenhydramine hydrochloride 1 mg/kg (max 50 mg) IV, dexamethasone 0.2 mg/kg (max 10 mg) IV (or equivalent), and other anaphylaxis medications as indicated. Epinephrine or bronchodilators should be administered as indicated. Hospital admission for observation may be indicated.

Discontinue ganitumab treatment permanently.

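### Section 6.4.2 orders corticosteroids stopped for hyperglycemia with no exception for steroids that cannot be stopped, and its action table does not literally cover the patients who need them

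*Combined protocol and SAP*

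**What the plan says.** Section 6.4.2 opens its hyperglycemia rules with an instruction to "discontinue use of corticosteroids before modifying ganitumab dose. If hyperglycemia occurs without use of corticosteroids, ganitumab therapy modifications should be as follows". The table that follows lets ganitumab continue at Grades 1 and 2. It requires a hold at Grade 3 or with glycosuria. At Grade 4 it requires a hold and a reduction to 12 mg/kg, with one absolute rule: "If associated with diabetic ketoacidosis or hyperosmolar nonketotic syndrome, discontinue ganitumab permanently".

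Other sections allow or call for corticosteroids during the study:

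- Section 3.2.1.1 bars pharmacologic systemic doses at entry except for CNS metastatic disease, and adds that "receipt of systemic physiologic replacement steroids, topical and/or inhaled corticosteroids is acceptable".
- Section 5.5.1.3 lists what is allowed on treatment, including "Physiologic replacement for patients with adrenal insufficiency" and "In patients with metastatic CNS disease, use of doses that have been stable or tapering since enrollment".
- Section 6.4.3, in its Grade 2 row, prescribes a steroid while ganitumab continues: "If Grade 1-2 infusion reactions reoccur with subsequent dose, add dexamethasone".

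The general toxicity rules sit behind these. Section 5.4.1 states that "DLT is defined as any of the following events that are possibly, probably or definitely attributable to palbociclib or ganitumab". Section 6.1 holds both drugs after such an event until Grade 1 or baseline, "and then palbociclib and ganitumab will be resumed with dose reduction", unless a specific toxicity section says otherwise.

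**The concern.** For a patient who can stop the steroid, 6.4.2 works as a sequence: stop it, then use the table. For a patient who cannot, the protocol does not say what to do. Two things follow from a literal reading.

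First, the stop order reaches steroids that the patient medically needs. Withdrawing adrenal replacement, or a dose that controls the effects of CNS metastases, is unsafe. Withdrawing infusion premedication contradicts 6.4.3.

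Second, if the site sensibly keeps the steroid going, the event is not one that occurs without corticosteroids, so the table is not triggered. The rule that ends ganitumab permanently after ketoacidosis or hyperosmolar syndrome is then lost for that patient, and it is stated nowhere else. At stake is possible re-exposure after a life-threatening metabolic event in one group, where every other patient has a mandatory stop.

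**Working it through.** No figure in the plan is in question and no arithmetic settles the point. The check sets the sections side by side and traces what happens to a patient.

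**1. When the stop order matters.** It is tied to modifying the ganitumab dose. Grades 1 and 2 require no modification, so the order matters mainly at Grade 3, at Grade 4, or with urine glucose above 0.1 g/dL.

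**2. Who cannot comply.**

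| Steroid | Where allowed or prescribed | Effect of the 6.4.2 order |
|---|---|---|
| Adrenal replacement | 3.2.1.1, 5.5.1.3 | Unsafe to stop |
| CNS metastases, stable or tapering dose | 3.2.1.1, 5.5.1.3 | Unsafe to stop abruptly |
| Dexamethasone premedication | 6.4.3 | Contradicts 6.4.3 when ganitumab is next given |

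No section reconciles these entries with 6.4.2.

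**3. Ketoacidosis in a patient not on a steroid.** The Grade 4 row applies and ganitumab stops for good. Under 6.1, permanent discontinuation of one agent removes the patient from protocol therapy altogether.

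**4. The same event in a patient whose steroid must continue.** The lead-in to the table is not met, so the other rules decide:

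- *Attributed at least possibly to study drug.* The event is a DLT under 5.4.1, since hyperglycemia is not among the listed exclusions. Section 6.1 holds both drugs until Grade 1 or baseline. Treatment then resumes at a reduced dose, which for ganitumab is 12 mg/kg (6.3). The patient comes off therapy if treatment cannot resume within 21 days.
- *Attributed to the steroid alone.* The event is not a DLT, and the 6.1 hold does not apply.
- *Either way.* Section 5.2.2, through 3.1.7.7, requires glucose of 160 mg/dL or lower without antihyperglycemic agents before each new cycle. It does not extend that requirement to the day 15 dose. Section 5.6 lets the investigator remove the patient by judgment. Section 6.4.2 also asks that treatment of hyperglycemia start under a pediatric endocrinologist's guidance.

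**5. Comparison.** Steps 3 and 4 differ in one respect that matters: permanent discontinuation is mandatory in step 3 and not in step 4. At Grade 3 the difference runs the other way. The table allows resumption at the same dose after timely recovery, whereas 6.1 reduces the dose, so falling back on 6.1 is not laxer there when the event is attributed to study drug.

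**6. Frequency.** The background section reports hyperglycemia in under 5% of patients in the adult phase 1 trial of ganitumab, with no related events of Grade 4 or higher, and related hyperglycemia of any grade in 5% in the phase 2 trial. Section 7.3 lists it at 10-20%. None of these is a Grade 3 or higher rate. The documents also do not give the share of patients on a steroid that cannot be stopped, or the frequency of ketoacidosis. Known type 1 or type 2 diabetes is an exclusion (3.2.11). A count of affected patients would be mostly assumption, so none is offered.

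**The case against.** The strongest reply is that this is a gap of literal wording that sensible sites would not fall into. The sentence sets an order of steps, and the specific permissions in 5.5.1.3 suggest that nobody intended replacement or CNS steroids to be withdrawn. A site faced with ketoacidosis would probably apply the Grade 4 row whatever the steroid status. Re-exposure would need recovery within 21 days where 6.1 applies and acceptable glucose off antihyperglycemics for a new cycle, with the treating team still choosing to resume. DLTs are reported immediately, and serious events within 24 hours, to the overall principal investigator. Restricting the table to events without steroids also has a rationale: it avoids penalizing ganitumab for a steroid effect.

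Most of this stands, and it limits the severity. It does not supply the missing instruction. A safety rule should not depend on sites reading past its text.

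The premedication group is also small. Dexamethasone is added only when reactions recur despite diphenhydramine, and it is given with a ganitumab dose. While ganitumab is held the patient is off that steroid and the table can be followed. What remains is a conflict when ganitumab is next given.

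A reader might infer that steroid users are unprotected after ketoacidosis. The documents do not support that: the DLT rule, the glucose criterion and investigator judgment all remain. A reader might also take the stop order to reach every patient with hyperglycemia of any grade. Its link to modifying ganitumab, and the instruction to continue at Grades 1 and 2, point to a much narrower reach.

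**Conclusion.** The point holds as a narrow drafting gap in a safety rule. In the rare patient whose hyperglycemia calls for a ganitumab change and whose corticosteroid cannot be stopped, the literal instruction is unsafe or conflicts with 6.4.3. The table, including the only mandatory permanent stop after ketoacidosis or hyperosmolar syndrome, does not literally apply. What remains is the 6.1 default if the event is attributed to study drug, the cycle-start glucose criterion, and judgment.

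Severity is low. No endpoint, error rate or sample size is affected. The conclusion rests on a literal reading of the lead-in to the table and on ordinary clinical judgment that replacement and CNS steroids should not simply be withdrawn. The documents do not support going further and holding steroid users to stricter ganitumab rules than other patients: their hyperglycemia has an alternative explanation, and the aim is equal coverage.

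**What to change.** Replace the opening instruction of 6.4.2 with wording such as: *Discontinue corticosteroids where medically safe (not physiologic replacement, steroids needed for CNS metastases, or premedication under 6.4.3). If hyperglycemia occurs without corticosteroids, persists after stopping them, or occurs in a patient whose corticosteroid cannot be stopped, modify ganitumab as follows.*

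The table itself stays as it is, so patients who must remain on a steroid are handled like everyone else, including the Grade 4 rule on ketoacidosis and hyperosmolar syndrome.

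The cost is two sentences in an amendment and no new assessments. The clinical price is that an occasional patient whose hyperglycemia is largely caused by the steroid may have ganitumab held. After ketoacidosis or hyperosmolar syndrome, that patient would lose protocol therapy altogether, because 6.1 does not allow continuation on palbociclib alone.

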#### *Non-Hematological DLT:*

- Any Grade 3 or higher non-hematological toxicity attributable to palbociclib or ganitumab with the specific exclusion of:
  - Grade 3 nausea and vomiting, anorexia, diarrhea or dehydration resolving to  $\leq$  grade 2 within 72 hours (note that grade 3 diarrhea requiring hospitalization would constitute DLT).
  - Grade 3 AST or ALT liver enzyme elevation that return to  $<$  grade 2 within 7 days (except as below if bilirubin also elevated). If grade 3 liver enzyme elevation occurs, palbociclib and ganitumab should be held and liver enzymes rechecked within 4 days of initial date of grade 3 abnormality to determine if DLT criteria have been met. See also Section 6.4.

**Recall:** For the purposes of this study the ULN for ALT is defined as 45 U/L and for AST is 30 U/L.

- Grade 3 hypophosphatemia, hypokalemia, hypocalcemia or hypomagnesemia responsive to oral supplementation within 72 hours.
- Grade 2 elevation of AST and/or ALT WITH total bilirubin  $> 2 \times$  ULN, in the absence of cholestasis.
- Any Grade 2 non-hematological toxicity that persists for  $\geq 7$  days and is considered sufficiently medically significant or sufficiently intolerable by patients that it requires treatment interruption.
- Any non-hematologic toxicity that results in delay in start of subsequent cycle by  $> 14$  days.

*Hematological DLT:*

- Hematological dose limiting toxicity is defined as:
  - Grade 4 thrombocytopenia or grade 4 neutropenia of any duration, in the absence of bone marrow disease; or
  - Grade 3 or higher febrile neutropenia with or without documentation of infection; or
  - Grade 3 thrombocytopenia in association with a grade 2 or higher bleeding episode; or
  - Delay in the start of subsequent cycle by  $> 14$  days due to thrombocytopenia or neutropenia, in patients without known bone marrow disease.

Patients with bone marrow metastatic disease at study entry will not be evaluable for hematologic DLT for the purposes of evaluating the toxicity monitoring rule. Such patients will follow the dose modification criteria in Section 6.2.1 in the setting of defined hematologic DLT.

Any Grade 5 toxicity that is possibly, probably, or definitely attributable to palbociclib or ganitumab will be considered a DLT.

Management and dose modifications associated with the above adverse events are outlined in Section 6.

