## 6.5 Dose Modifications for Hematologic Toxicity

Hematologic toxicity is considered an adverse event with the use of palbociclib and has also been reported less commonly with IGF-1R monoclonal antibodies, including ganitumab. Palbociclib dose modifications are outlined in Sections 6.5.1. Ganitumab should be held if a patient meets criteria for hematologic DLT per Section 5.4.1. For a patient's first hematologic DLT, palbociclib will be dose reduced, but ganitumab may be resumed without dose modification once the patient meets criteria to resume palbociclib according to **Table 8 or 9**. For recurrent hematologic DLTs despite one palbociclib dose reduction, ganitumab should be resumed at a lower dose according to **Table 2** in addition to any additional required dose reductions for palbociclib.

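### The hyperglycemia rule in Section 6.4.2 sets the reduced ganitumab dose at a fixed 12 mg/kg, which is no reduction for a patient already on 12 mg/kg, where Section 6.1 points to removal

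*Combined protocol and SAP*

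**What the plan says.** Table 2 (Section 6.3) starts ganitumab at 18 mg/kg and lists one reduction, to 12 mg/kg.

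Section 6.4.2 uses that figure as an absolute dose in two rows:
- **Grade 3** that recurs despite a stable dose of insulin or an oral agent, or that needs more than 2 weeks of interruption: "subsequent doses should be administered with a reduced dose of 12 mg/kg/dose". The row has no stopping clause.
- **Grade 4** without ketoacidosis or hyperosmolar syndrome: "Resume ganitumab with a reduced dose of 12 mg/kg/dose IF patient is asymptomatic", with conditions on glucose, glycosuria and resolution within 2 weeks. Ganitumab stops for good in three cases: ketoacidosis or hyperosmolar syndrome, resolution taking more than 2 weeks, or recurrence ("if Grade 4 toxicity recurs after re-challenge with 12 mg/kg, then discontinue ganitumab permanently").

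Section 6.1, the general DLT rule, says: "If a second dose reduction is required for toxicity related to ganitumab, the patient will be removed from protocol therapy". It also removes a patient who cannot resume within 21 days, and one whose DLT recurs despite two palbociclib reductions. Its hold-and-resume sentence defers to later sections: "Except where noted below for specific target toxicities, palbociclib and ganitumab will be held until resolution of toxicity".

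Section 5.4.1 counts as a DLT "Any Grade 3 or higher non-hematological toxicity attributable to palbociclib or ganitumab with the specific exclusion of" a short list that does not mention hyperglycemia. Attributable Grade 3 or higher hyperglycemia therefore falls under 6.1 as well as 6.4.2.

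**The concern.** A reduction written as a fixed dose works only from the starting dose. The protocol treats these hyperglycemia events as needing less ganitumab, yet for a patient already on 12 mg/kg the instruction leaves the dose unchanged. Section 6.1 suggests that the same patient should come off therapy. Two investigators could each follow the protocol and do opposite things.

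What is at stake is patient handling: re-exposure to the dose on which severe hyperglycemia occurred, in a combination not studied before and in patients from age 12.

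**Working it through.** There is no plan figure to reproduce. The check sets the rules side by side.

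**Size of the step.** From 18 mg/kg: 1 − 12/18 = 33%. From 12 mg/kg: 1 − 12/12 = 0%.

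**How a patient comes to be on 12 mg/kg under present dosing.**
1. A non-hematologic DLT handled under 6.1 and 6.3.
2. A recurrent hematologic DLT under 6.5: "For recurrent hematologic DLTs despite one palbociclib dose reduction, ganitumab should be resumed at a lower dose according to" Table 2. This is clear in Cohort B. In Cohort A it is less so, because Table 1 has no second palbociclib step.
3. Earlier Grade 3 hyperglycemia (6.4.2).
4. Earlier Grade 4 hyperglycemia (6.4.2).

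**What each section then directs.**

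| Event on 12 mg/kg | 6.4.2 read alone | 6.1 |
|---|---|---|
| Grade 3, recurrent on stable insulin or oral agent | 12 mg/kg again; no stop in the row | Removal, if a second reduction counts as required |
| Grade 3, more than 2 weeks to resolve | 12 mg/kg again; no stop in the row | As above; removal in any case if therapy cannot resume within 21 days |
| First Grade 4, uncomplicated, resolved within 2 weeks | Resume at 12 mg/kg | Removal, if a second reduction counts as required |
| Grade 4 recurring after re-challenge at 12 mg/kg | Stop | Removal |
| Grade 4, more than 2 weeks to resolve | Stop | Removal |
| Grade 4 with ketoacidosis or hyperosmolar syndrome | Stop | Removal |

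The last three rows agree, because 6.1 ends protocol therapy once either agent is permanently stopped. The first three are the gap. The clearest case lies wholly within 6.4.2: a patient is reduced to 12 mg/kg for recurrent Grade 3 and then has a first Grade 4 event. That event is not a Grade 4 recurrence, so the row's stop does not apply and the dose given is 12 mg/kg.

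**Contingency C (Section 5.4.2).** If it were enacted, patients would start at 12 mg/kg. Every 6.4.2 reduction would then be empty. The 6.1 sentence would not strictly apply either, because this would be their first reduction.

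**Number of patients (illustrative).** The documents give hyperglycemia rates only for any grade: below 5% in the adult phase 1 trial, 5% related in the ganitumab phase 2 trial (both Section 2.2.1.2), and 10-20% in monotherapy studies (Section 7.3). Planned evaluable patients: 15 + 12 = 27. As a stand-in for the number reaching 12 mg/kg, take the two DLT rates in Section 13.4: 27 × 0.09 = 2.4 and 27 × 0.39 = 10.5, so 2 to 10. Assume that 1% to 5% of these then have a triggering event.
- Expected: 2 × 0.01 = 0.02 to 10 × 0.05 = 0.5. At an assumed 10% event rate, 10 × 0.10 = 1.0.
- Chance of at least one: 1 − 0.99² = 2% to 1 − 0.95¹⁰ = 40%.

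**The case against.** The strongest reply is that 6.1 already answers the question. Its removal sentence carries no exception; the deferral to specific toxicities opens a different sentence. Table 2 labels 12 mg/kg as the first reduction, so a reduced dose of 12 mg/kg is naturally read as a step from 18, with 6.1 governing afterwards. This stands as the better reading of intent. It does not close the gap. Removal is triggered only when a second reduction is required, and 6.4.2 requires only 12 mg/kg. The Grade 4 row stops for recurrence only after re-challenge at that dose. It is also unclear whether an earlier ganitumab reduction for a hematologic DLT counts as the first one for ganitumab toxicity.

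A reader might infer that a patient on 12 mg/kg has no way off treatment. The documents do not support that. The 21-day limit leaves the slow Grade 3 case only the interval between 14 and 21 days. The recurrent-DLT rule adds a bound, though it counts palbociclib reductions. Section 5.6 allows removal on the investigator's judgment.

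A reader might also count route-by-event combinations and conclude that nearly all lack an exit. The four routes and the three events sent to 12 mg/kg give 12 combinations, 11 of them without an exit in 6.4.2. Adding the two Grade 4 events that always stop gives 20 combinations, with 9 exits. The fraction depends on the denominator chosen and should not be used.

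Safeguards also reduce the harm. Resumption after Grade 4 needs an asymptomatic patient with glucose consistently below 250 mg/dL and no glycosuria. Insulin is allowed, and treatment starts under an endocrinologist. DLTs are reported at once to the overall principal investigator. Known diabetes and baseline glucose above 160 mg/dL are excluded.

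**Conclusion.** The point holds and is minor. For a patient already on 12 mg/kg, 6.4.2 read literally repeats the dose in three situations where 6.1 points to removal. Conflicting actions for one patient are more than missing detail in a safety rule, but the case is rare.

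Probably fewer than one patient is affected. That rests on assumed inputs, since no Grade 3-4 rate is given. The 40% at the top of the range should not be read as a forecast. It stacks an assumed event rate on 39%, which is the unacceptable DLT rate in Section 13.4. Enrollment pauses at 3 cycle 1 DLTs among up to 12 patients in a cohort, and a first hematologic DLT leaves ganitumab unchanged. Later-cycle DLTs could add patients, at a rate the documents do not give.

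A reader might infer that the trial's conclusions are at risk. They are not: the design properties of the response test and of the cycle 1 DLT rule do not depend on how ganitumab is re-dosed after hyperglycemia.

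**What to change.** In both cells of 6.4.2, replace the fixed dose with: *reduce ganitumab by one dose level per Table 2; if already at 12 mg/kg, remove from protocol therapy (Section 6.1)*. Keep the other conditions in those cells. State that this also applies to patients who start at 12 mg/kg under Contingency C. The QTc table in 6.4.1 is a model: it steps down from the current dose and removes the patient once the reductions are used up.

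The cost is wording in two cells and one added sentence, with no extra patients, visits or analyses. The downside is that a rare patient who might have continued on 12 mg/kg with insulin cover comes off therapy, which 6.1 already implies for patients reduced from 18 mg/kg.
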